8. REFERENCES

Not Applicable.

9. APPENDICES

Appendix 1. Definition and Use of Visit Windows in Reporting

Visit windows will be used for efficacy and patient/observer reported outcomes variables that display or summarize by study visit.

Visit Label	Target Day	Definition [Day window relative to Study C3291027 Day 1]
Screening/Baseline of qualifying parent study		
Week 4	29	Days 16 to 43
Week 8	57	Days 44 to 71
Week 12	85	Days 72 to 99
Week 16	113	Days 100 to 127
Week 20	141	Days 128 to 155
Week 24	169	Days 156 to 183
Week 28	197	Days 184 to 211
Week 32	225	Days 212 to 239
Week 36	253	Days 240 to 267
Week 40	281	Days 268 to 295
Week 44	309	Days 296 to 323
Week 48	337	Days 324 to 351
Week 52	365	Days 352 to

If two or more visits fall into the same window, keep the one closest to the Target Day. If two visits are equaled distant from the Target Day in absolute value, the later visit should be used.

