Visit Window		±7 days based on Day 1			±7 days based on Day 1	+7 days based on Week 52/EOT/ET
Contraception check g	X	X	X		X	X
Study intervention						
Body Site Checklist of AD lesions	X	X		X	X	
Record treatable AD areas	X	X		X		
Study Intervention Dispensing h	X i	X		X		
Instruction for dosing and dispense dosing diary	X i	X		X		
Weigh the investigational product tube(s) and dispense	X i	X		X		
Study intervention administration	X i	BID, throughout On-Treatment Cycle j,k		BID, for the remainder of a treatment cycle j,k		
Review dosing diary; assess compliance		X l	X l		X l	
Collect and weigh returned investigational product tubes, including empty, partially used and unused tubes		X l	X l		X l	
Assessments						
Calculate and record treatable %BSA	X e	X	X	X	X	
ISGA m	X e	X	X	X	X	
Regional ISGA-face m,o	X e	X	X		X	
EASI m	X e	X	X		X	

Visit Identifier a Abbreviations used in this table may be found in Appendix 6 .	Enrollment Visit	Intervention Period				Follow-up Contact b
	Visit 1	Visit 2-13		Unplanned Visit to initiate study intervention during Off-Treatment Cycle	Visit 14	Visit 15
	Day 1 c	Weeks 4, 8, 12, 16, 20, 24, 28, 32, 36, 40, 44, 48			Week 52/EOT/ET	Week 56/EOS
		Days 29, 57, 85, 113, 141, 169, 197, 225, 253, 281, 309, 337			Day 365/EOT/ET	Day 393/EOS At least 28 days after last study dose
Visit Window		±7 days based on Day 1			±7 days based on Day 1	+7 days based on Week 52/EOT/ET
Peak Pruritus NRS/Patient Reported Itch Severity Scale/ Observer Reported Itch Severity Scale n	X e	X	X		X	
Concomitant treatment(s)	X e	→	→	→	→	X
Serious and nonserious adverse event monitoring	X e	→	→	→	→	→
Review lifestyle considerations	X	X	X		X	X
Schedule/reconfirm next study visit or contact	X	X	X		X	
Remind to bring all investigational product tubes and the dosing diary to the next visit	X i	X	X p	X		
Blood sampling to obtain plasma for crisaborole and metabolites PK	X q					

- Day relative to start of study intervention (Day 1).
- Contact may occur via telephone contact and must occur 28 to 35 days from Week 52/EOT/ET Visit.

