### **7.2. Participant Discontinuation/Withdrawal From the Study**

A participant may withdraw from the study at any time at his/her own request. Reasons for discontinuation from the study include the following:

- Refused further follow-up;
- Lost to follow-up;
- Death;
- Study terminated by sponsor;
- The occurrence of AEs that require the participant to stop participation in the study, due to availability for, or intolerance to, the study procedures;
- AEs that are considered to be clinically significant by the investigator and/or physician in charge, and/or might be harmful to the participant's health;
- Need the continuous rescue therapy for >28 days;
- Concurrent disease that requires use of a prohibited medication.

At the time of discontinuing from the study, if possible, an early discontinuation visit should be conducted. See the [SoA](#) for assessments to be collected at the time of study discontinuation and follow-up and for any further evaluations that need to be completed.

The early discontinuation visit applies only to participants who are enrolled/randomized and then are prematurely withdrawn from the study. Participants should be questioned regarding their reason for withdrawal.

The participant will be permanently discontinued both from the study intervention and from the study at that time.

If a participant withdraws from the study, he/she may request destruction of any remaining samples taken and not tested, and the investigator must document any such requests in the site study records and notify the sponsor accordingly.

If the participant withdraws from the study and also withdraws consent (see Section 7.2.1) for disclosure of future information, no further evaluations should be performed and no additional data should be collected. The sponsor may retain and continue to use any data collected before such withdrawal of consent.

Lack of completion of all or any of the withdrawal/early termination procedures will not be viewed as protocol deviations so long as the participant's safety was preserved.

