1. VERSION HISTORY

Table 1. Summary of Changes

Version/ Date	Associated Protocol Amendment	Rationale	Specific Changes
1 4 Aug 2020	Original 20 May 2020	N/A	N/A
2 7 Jan 2021	Original 20 May 2020	Study termination	Updated the following analyses due to the small sample size and the short exposure period. 6.4. Subset Analyses 6.5.3. Study Treatment Exposure 6.5.4. Concomitant Medications and Nondrug Treatments 6.6.1. Adverse Events

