2.2. Study Design

This study is a Phase 3, multicenter, open-label, long-term safety extension study of Studies C3291032 and C3291031 in Japanese pediatric and adult participants with mild to moderate AD to support the registration of crisaborole in Japan. After completion of the study intervention period in Study C3291032 or Study C3291031 and confirmed Study C3291027 eligibility, participants will be offered participation in the study from investigator sites in Japan. The sample size of this study is approximately 150 participants but will be determined by the number of participants who complete Study C3291032 treatment period or

Study C3291031 treatment period and meet eligibility criteria of this study. Scheduled study visits will occur every 4 weeks (1 cycle) with On-Treatment or Off-Treatment cycles to be decided by the investigator based on the ISGA score. PK blood sampling will be conducted at the selected study sites for the participants aged between 2 years old and 11 years old at the time of signing the ICD in Study C3291032.

When the investigator assessment of ISGA is Almost Clear (1) or greater, an On-Treatment Cycle will be initiated. When the investigator assessment of ISGA is Clear (0), crisaborole ointment, 2% treatment will not be initiated and the participant will enter an Off-Treatment Cycle. Based on the ISGA score throughout the study, a participant may be administered a variable number of cycles of crisaborole ointment, 2% treatment (On-Treatment Cycle) during their up to 52 weeks of study participation.

On Week 56 (End of Study), a follow-up telephone call will be made by site staff to assess for AEs that may have occurred since the last visit.

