5.3. Methods to Manage Missing Data

In general, for analyses using descriptive statistics, missing values will not be imputed. In addition, for safety endpoints, missing values will not be imputed. Other methods for handling missing values are discussed below.

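### SAP Appendix 1 has no EOT/ET row, so early-termination scores taken soon after a scheduled visit, or on Days 2-15, enter no by-visit EASI, ISGA, %BSA, face or itch summary

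*SAP*

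**What the plan says.** The Protocol's Schedule of Activities (1.3) treats Week 52, EOT and ET as one visit. ISGA, Regional ISGA-face, EASI, treatable %BSA and itch are all collected there. For participants who leave early, Protocol 7.2 adds: "At the time of discontinuing from the study, if possible, an early discontinuation visit should be conducted". That visit has no target day of its own. Regular visits are four weeks apart, with a tolerance of ±"7 days based on Day 1".

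SAP Appendix 1 sets the reporting rule: "Visit windows will be used for efficacy and patient/observer reported outcomes variables that display or summarize by study visit". Its table gives windows from Week 4 (Days 16 to 43) to Week 52 (Day 352 onward). Where visits collide, "If two or more visits fall into the same window, keep the one closest to the Target Day"; and "If two visits are equaled distant from the Target Day in absolute value, the later visit should be used". The table has no EOT/ET row.

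SAP 6.3.1 and 6.3.2 summarise EASI, ISGA, %BSA, Regional ISGA-face and itch over time. SAP 5.3 states: "In general, for analyses using descriptive statistics, missing values will not be imputed". No last-assessment summary is planned. Protocol 9.4.4.1 says that the efficacy measures are to be summarised at every visit at which they were taken.

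SAP version 2 (7 Jan 2021) was issued because the study was terminated: "Updated the following analyses due to the small sample size and the short exposure period". Appendix 1 is not among the sections it lists as changed.

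**The concern.** The ET assessment is a planned, complete efficacy assessment made as the participant leaves. Under Appendix 1 it competes on study day with the preceding scheduled visit and, if that visit was on time, loses to it for the next 14 days. An observed score then disappears from the tables, although nothing is missing.

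For a participant who leaves with worsening atopic dermatitis, the lost score is the unfavourable one. At stake is whether the report can show the state in which participants ended. In a small study stopped early, a few such scores could be a visible share of the data.

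**Working it through.** **Inputs.** Target days are 29, 57, ..., 365 and windows are as in SAP Appendix 1. Visit tolerance is ±7 days (Protocol 1.3). The plan gives no figure for ET loss, so there is none to reproduce. As a check, target −13 to target +14 reproduces all 12 closed windows (Week 8: 57 − 13 = 44 and 57 + 14 = 71).

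**What the rule does**
- *Dropped.* Scheduled Week 8 visit on Day 57, ET on Day 64. Both lie in Days 44-71, at distances 0 and 7. Day 57 is kept. Day 64 is not used, and nothing falls in the Week 12 window.
- *Replaces the scheduled visit.* Scheduled visit on Day 50, ET on Day 60. The distances are 7 and 3, so the ET is kept and the scheduled score is dropped. With the ET on Day 64 the distances tie at 7, and the later visit, again the ET, is used.
- *Kept under a later label.* An ET on Day 72 becomes the Week 12 value.
- *No window.* The first window opens on Day 16, so an ET on Days 2-15 goes nowhere.

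**Share dropped.** Assumption, not in the documents: the ET day is uniform over the days strictly between the last attended scheduled visit and the next one. Let j be the number of days by which the last scheduled visit missed its target (negative if early). After Week 4:
- dropped days = 14 − |j|
- days on which the ET replaces the scheduled visit = 2|j| if j < 0, otherwise 0
- kept days under the next label = 13, if the next visit is due on target

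| Last scheduled visit | Dropped / between-visit days | Share |
|---|---|---|
| on target | 14/27 | 52% |
| 3 days early | 11/30 | 37% |
| 7 days early | 7/34 | 21% |
| 3 days late | 11/24 | 46% |
| 7 days late | 7/20 | 35% |

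If scheduled visits vary uniformly over ±7 days, the mean of |j| is 56/15 = 3.73 and the mean number of between-visit days is 27:
- dropped: (14 − 3.73)/27 = 38.0%
- replaces the scheduled visit: 3.73/27 = 13.8%
- kept under the next label: 13/27 = 48.1%

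With ±3 days, 45.5% are dropped; with ±5 days, 41.8%.

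Over all 13 intervals (13 × 27 = 351 days), the rule drops 12 × 14/351 = 47.9% on target and 12 × 10.27/351 = 35.1% with ±7 days. Days 2-15 add 14/351 = 4.0%, for totals of 51.9% and 39.1%. Within the first interval alone, 14 of 27 days (52%) have no window.

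**Sensitivity to timing.** An ET held at a scheduled visit does not collide. If 25%, 50% or 75% of ETs are of that kind, 52% falls to 39%, 26% or 13%, and 38% falls to about 29%, 19% or 10%.

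**As a share of all final scores.** Multiply by the proportion of participants who end with a between-visit ET. At 10% the loss is 4-5% (0.10 × 38% to 52%), at 50% it is 19-26%, and at 100% it is 38-52%.

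**Early termination.** From 20 May 2020 (Protocol) to 7 Jan 2021 (SAP version 2) is 232 days, so no participant could have reached Day 365 by then.

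**The case against.** The case for leaving the rule alone is substantial. The affected endpoints are exploratory and descriptive, in a single-arm study whose primary endpoint is safety, which the windows do not touch. No listed endpoint asks for end-of-treatment status, and closest-to-target is a prespecified rule with a tie-break.

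A reader might infer that by-week response is biased upward. The documents do not support that. In the Day 57/64 example, Day 57 is the correct Week 8 value, and putting an event-triggered Day 64 score in its place would itself distort Week 8. The participant's absence from Week 12 onward is an observed-case matter that this rule does not create.

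Flare exits also need not be timed uniformly. Under Protocol 6.5.3 and 7.1, leaving for continuous rescue comes only after more than 28 days, so a scheduled visit would ordinarily fall within the rescue period and record the flare. ETs caused by the sponsor's termination are not triggered by worsening, so their loss has no expected direction.

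These points limit the size and direction of the claim. They do not answer the loss itself: scores are collected, Protocol 9.4.4.1 says they will be summarised, and no planned summary of these endpoints contains them. Short exposure does not remove the problem, because before Week 4 the gap on Days 2-15 loses the same 14 of 27 days.

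**Conclusion.** The point holds as a gap in the reporting rule. That an ET 1-14 days after an on-target visit is dropped, and that one on Days 2-15 has no window, follows from Appendix 1 without any assumption. The size does not: roughly 35-52% of between-visit ET assessments are dropped under uniform timing, and the share is lower if many ETs coincide with scheduled visits or if the last visit was well early (21% at 7 days early).

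Two further inferences should be resisted. The percentage does not apply to final scores in general, since a Week 52 score on schedule is kept and neither document gives the proportion of participants with an ET. Nor are the scores absent from every efficacy summary in the sense of the participant vanishing: rescue-medication incidence (SAP 6.3.1.9) is not tied to a visit and is unaffected.

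What is lost is end-of-participation status, unfavourable for those leaving with worsening disease. That most final assessments here are ET visits is likely from the dates and the stated short exposure, but the documents give no counts. The change is worth making; it does not bear on the primary analysis.

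**What to change.** Add one row to SAP Appendix 1, named EOT/ET (last on-study assessment). Fill it from each participant's Week 52/EOT/ET visit whatever the study day, and state that it is exempt from the closest-to-target rule. Summarise EASI, ISGA, treatable %BSA, Regional ISGA-face and itch at that row beside the unchanged by-week rows, with the median and range of study day.

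This brings the loss of ET scores to zero, including Days 2-15, and displaces no scheduled visit. Giving the ET precedence within its window would do neither fully: Days 2-15 would stay uncovered and on-target weekly values would be overwritten.

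The cost is one row and one sentence in the SAP and one extra column per table; no new data are needed. The downside is that the row pools different times on study, which is why the day range must be shown.
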